**(This space intentionally left blank.)**

**Purposes:**

1. To analyze the outcomes of patients treated with coccygectomy for coccygodynia and report on the rate of complications of this procedure.
2. To find pre-operative clinical predictors of good outcomes after coccygectomy.

**Null Hypotheses:**

1. Coccygectomy will not improve scores on the SF-36, ODI, tolerable sitting time, or VAS.
2. There are no independent variables associated with improved outcomes.

**Background and Significance:**

The term coccygodynia was coined in 1859 by Simpson to describe the symptoms of pain in the area of the coccyx. “Coccyx” is derived from the word “cuckoo” because of its resemblance to a bird’s beak (4). This region represents the terminal end of the spinal column and consists of three to four fused coccygeal vertebral segments. Patients with pain in this area have a higher incidence of sacrococcygeal fusion and more angular sagittal alignment of the coccyx compared to asymptomatic patients. Coccygodynia is five times more prevalent in women than men. The mean age of onset is 40 years, but can occur through a wide range of ages. Coccygodynia has many causes. It can begin insidiously and have no history of trauma. It can also begin after a fall with a contusion over the buttock or after a difficult vaginal delivery. Obesity is also three times more common in patients with coccygodynia than in the general population.

*Clinical presentation:*

The main clinical symptom is pain. Pain may slowly progress insidiously or begin acutely after a traumatic event. Typically pain is localized directly over the coccyx with no associated low back pain or referred pain. Sitting is typically the worst position for these patients and pain with defecation or sexual activity is common. Physical examination typically reveals tenderness to palpation at the coccyx. Rectal exam may reveal a tender, mobile, distal coccygeal segment.

*Imaging:*

Much attention has been paid to the radiographic findings in coccygodynia. Postacchini and Massobrio reported that single position radiographs seldom show differences between normal individuals and those with coccygodynia (9). Maigne et al compared standing and sitting radiographic views of the coccyx in a total of 582 patients with coccygodynia and found abnormalities in 70% of the patients (7) (figure 1). Hypermobility of greater than 25 degrees, posterior subluxation of a mobile segment, or a coccygeal spicule can all be seen with sitting radiographs and are consistent with coccygodynia (figure 2).

*Non-operative Treatment:*

All patients presenting with coccygodynia should be initially treated conservatively. Treatment modalities include non-steroidal anti-inflammatory and analgesic medications,

rest, and cushion support. Rarely, physical therapy with diathermy and ultrasound may be prescribed, although there is no evidence to support its role. After initial conservative management, corticosteroid injections may be performed. Wray et al reported a cure rate of 59% with local steroid injection alone, and an 85% cure rate when injection was combined with manipulation under anesthesia. There was a 21% relapse rate in this group of patients (11). Maigne and Chatellier attempted conservative treatment with levator ani muscle massage, joint mobilization and stretching exercises and found only a 25% success rate (7).

*Surgical Treatment:*

When conservative treatment for coccygodynia fails, removal of the coccyx (coccygectomy) may be considered. Both significant, disabling pain and radiographic abnormalities should be present before surgical consideration. Surgery consists of either complete removal of the coccyx or excision of the mobile segment. The most common complication is wound infection and dehiscence due to perineal contamination (8, 10). Maigne et al prospectively followed 37 patients treated with coccygectomy and found 34 of 37 had good to excellent results at minimum of 2 years. Doursounian et al reported on 61 patients treated with coccygectomy, which is the largest retrospective case series published (3). They found good to excellent results in 53 of 61 patients. Nine patients in this study developed an infection requiring re-operation. Wood and Mehbod compared 20 patients treated with coccygectomy to 25 patients treated with corticosteroid injections. They found 90% of patients treated surgically felt improvement whereas only 20% of patients treated with injections felt improvement. This study however was not randomized and decision to treat operatively was made by the senior author leading to significant selection bias.

**Summary:**

Coccygodynia can be a functionally limiting and painful disease with conservative treatment providing mixed results. When proper surgical indications are met, results seem to be promising. However, there is a lack of data in the literature to support surgical treatment. The case series reports currently in the literature are small and retrospective with ill-defined selection criteria. To date there has been no study prospectively following patients undergoing coccygectomy. This type of study could accurately obtain data prospectively. This information will help better guide the clinician through treatment of this disease.

**Study Design**

**A) Summary of Study Design:**

All patients will be seen and enrolled through an outpatient spine specialty clinic of the senior author. Patients that meet the inclusion criteria will be offered enrollment in the study by a third party (clinical research assistant). Patients enrolled will then complete pre-treatment SF-36, Oswestry Disability Scale and a pain visual analog scale. Patients will be followed at 2 weeks, 6 weeks, 3 months, 6 months, 1 year and 2 years after treatment. Patients will complete the

questionnaire containing the VAS and tolerable sitting time at all visits with SF-36 and Oswestry disability scale completed at one year post treatment.

**B) Type of Study:** Prospective Observational Study

**C) Study Population**

a. **Inclusion Criteria**

- i. Pain in the region of the coccyx
- ii. Pain for greater than 2 months
- iii. Tenderness to palpation over coccyx
- iv. Radiographic abnormalities of the coccyx
  - 1. Hypermobility of greater than 25 degrees, posterior subluxation of a mobile segment, or a coccygeal spicule on sitting radiographs

Or

- 2. post-traumatic coccygodynia

- v. Failure of conservative treatment methods: 4 weeks of NSAIDS, seat cushion, and rest
- vi. Partial coccygectomy

b. **Exclusion Criteria**

- i. Coexisting low back pain
- ii. Total previous coccyx surgery or previous lumbar fusion
- iii. Under 18 years of age

c. **Method of Selection:** Patients will be deemed study candidates by the senior author.

d. **Sample's representation of total population:** All subjects presenting to our specialty clinic that meet the selection criteria will be offered enrollment. This should represent the total population of patients with this disease.

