**D) Definition of Variables**

- a. **Outcome Variables:** Visual Analog Scale for pain intensity, Short-Form 36, Oswestry Disability Scale, Tolerable sitting time, wound complications, intra-operative complications
- b. **Independent Variables:** Age, gender, co-morbidities, type of coccygeal morphology
- c. **Potential Confounding Variables:** Disability status, pain medications prescribed by other physicians, co-existing musculoskeletal disease.

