### *Coccygectomy*

The surgical procedure will be performed at a tertiary care center in an operating room suite. Pre-operatively, patients will complete a dulcolax suppository and will receive pre-operative dose of first generation cephalosporin, vancomycin, or clindamycin for antibiotics. Patients will be placed under general anesthesia and positioned in knee-to-chest position. An incision will be made directly over the coccyx and cautery dissection will be used to identify the terminal mobile segment. The mobile segment will be removed and will be sent for pathology. The wound will be irrigated and closed in two layers with dermabond placed over the incision. Patients will be discharged home the day of surgery if appropriate. Postoperatively, patients will be placed on milk of magnesia and will sit in a donut cushion seat until seen at clinic follow-up two weeks post-operatively.

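### Eligibility does not carry over the background's surgical indication, and traumatic onset, the second entry route, is not a listed variable, so normal versus abnormal morphology would be confounded with onset

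*Combined protocol and SAP*

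**What the plan says.** - **Background and Significance, surgical treatment:** "Both significant, disabling pain and radiographic abnormalities should be present before surgical consideration".
- **C) Study Population, inclusion criteria:** the pain criteria cover site, tenderness and duration ("Pain for greater than 2 months"). No VAS, Oswestry or other severity level is set. Criterion iv is headed "Radiographic abnormalities of the coccyx" and gives two options joined by *or*. The first is "Hypermobility of greater than 25 degrees, posterior subluxation of a mobile segment, or a coccygeal spicule on sitting radiographs". The second is "post-traumatic coccygodynia".
- **Coccygectomy:** after the terminal mobile segment is identified, "The mobile segment will be removed and will be sent for pathology".
- **D) Definition of Variables:** the independent variables are "Age, gender, co-morbidities, type of coccygeal morphology". Onset and route of entry are not among them or among the listed confounders.
- **Coccygodynia Questionnaire (Figure 6):** asks about pain, pain medicines and sitting. It has no item on trauma.
- **Radiographs; Summary of Study Design:** seated and standing films are taken on every enrolled patient and read against published criteria. SF-36, Oswestry and VAS are collected before treatment.
- **Purposes; Statistical Procedures:** Purpose 2 seeks pre-operative predictors of good outcome. The analysis section specifies descriptive statistics, a pooled before/after rank test and complication rates. It names no predictor or subgroup analysis.

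**The concern.** The background gives two conditions that should both hold before surgery is considered, and the eligibility list reproduces neither plainly. Pain has no severity requirement, and the film requirement has an alternative defined by history. The operation is described as removal of a mobile segment, but the text does not say that a patient entering through a spicule or through trauma has one.

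The statistical stake lies in Purpose 2. If the second option admits patients with normal films, those patients differ from the rest in two ways at once: they have no listed abnormality, and they all have a traumatic onset. Morphology is a listed predictor and onset is not. A difference between normal and abnormal films could then be credited to morphology when it belongs wholly or partly to onset, or a real morphology difference could be masked. Staff must establish trauma for patients who enter by the second option. Nothing requires them to ask about it in patients who already qualify on film, so the information needed to separate the two may be missing where it is needed most.

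**Working it through.** **1. Three readings of criterion iv.**

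| Reading of the second option | Role of *or* | Patients without a listed finding |
|---|---|---|
| No film finding needed (literal) | Works as written | Eligible, all post-traumatic |
| Some other, unlisted abnormality needed (from the heading) | Works, but the abnormality is undefined | Eligible, all post-traumatic |
| A listed finding still needed | Does nothing | Not eligible |

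The heading leaves the text ambiguous. Only the third reading removes the problem, and it leaves the second option without a function.

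**2. Which patients can exist under the first two readings.**

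| | Traumatic onset | Non-traumatic onset |
|---|---|---|
| Listed abnormality | eligible | eligible |
| No listed abnormality | eligible | not eligible |

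**3. What a crude morphology comparison estimates.** Let *a* be the mean outcome with normal films and non-traumatic onset, *b* the difference for abnormal films, *g* the difference for traumatic onset (effects taken as additive), and *t* the fraction of abnormal-film patients with traumatic onset.

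- Mean with abnormal films: a + b + t·g
- Mean with normal films: a + g
- Crude difference: (a + b + t·g) − (a + g) = b − (1 − t)·g

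The bias is −(1 − t)·g: zero at t = 1, half of *g* at t = 0.5, and all of *g* at t = 0. The documents give neither *t* nor *g*.

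With onset recorded, *b* can be estimated within post-traumatic patients and *g* within abnormal-film patients, provided t lies between 0 and 1. Because the fourth cell is empty, an interaction between the two cannot be estimated.

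**4. How many patients might enter without a listed abnormality.** The documents give no figure. The only related one is that a cited series of 582 patients with coccygodynia "found abnormalities in 70% of the patients". That series was not restricted to surgical candidates. As an assumption only, let 70% apply here and let *q* be the fraction of normal-film patients with trauma. The share is 0.30q / (0.70 + 0.30q):

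- q = 0: 0%
- q = 0.5: 0.15 / 0.85 = about 18%
- q = 1: 0.30 / 1.00 = 30%

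**5. Precision of a comparison by route.** First, the plan's own figure. Noether's formula with two-sided alpha 0.05, 90% power, equal groups and p'' = 0.70 gives N = (1.960 + 1.282)² / [12 × 0.5 × 0.5 × (0.70 − 0.50)²] = 87.56, or 43.8 per group, rounded up to 44. This matches the plan. Then 44 / 0.88 = 50 matches its allowance for loss.

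For an unequal split with a share *c* in the smaller group and *n* evaluable patients, power = Φ(√[12·c·(1 − c)·n] × 0.20 − 1.960). At n = 88 and c = 0.10: √95.04 = 9.75; 9.75 × 0.20 − 1.960 = −0.01; power is about 50%.

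| Share in smaller group (assumed) | n = 88 | n = 44 |
|---|---|---|
| 10% | 50% | 28% |
| 20% | 74% | 45% |
| 30% | 85% | 56% |
| 50% | 90% | 63% |

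Here 88 is the plan's two groups of 44 taken as separate patients, and 44 applies if the two groups are one cohort measured before and after. The unconfounded comparison, within post-traumatic patients, leaves some abnormal-film patients out. At the same p'' and the same number of normal-film patients its power is therefore lower than shown.

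**The case against.** The strongest reply has four parts.

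- **The data to separate patients are already there.** A reader might infer that a mixed population is pooled with nothing to tell its parts apart. The documents do not support that. Every patient has classified films, morphology is a listed predictor, and baseline VAS and Oswestry are collected, so normal-film and low-pain patients can be identified. This stands, and it limits the gap to onset.
- **The text may still require an abnormality.** Both options sit under a heading about radiographic abnormality, so it would be wrong to state as fact that normal-film patients are admitted. This also stands. The point rests on the literal reading or on the unlisted-abnormality reading.
- **The study is observational.** A reader might infer that enrolment exposes patients to an operation that the document's own indication does not support. Partial coccygectomy is itself an inclusion criterion, the background sentence is narrative, and failed conservative treatment and the senior author's judgement also apply. The documents show an inconsistency, not harm.
- **No predictor analysis is specified for any variable,** so adding one more to the list changes nothing by itself. This is correct, and it is why the fix must also name the analysis. It does not remove the confounding that such an analysis would meet.

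That the operation may not fit every entrant is an inference from the alternatives in criterion iv. No section says that spicule or post-traumatic patients lack a mobile segment. It is a reason to reconcile the sections and no more.

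**Conclusion.** The point holds in this form. The background indication, the inclusion criteria and the description of the operation do not agree and must be reconciled; which is clinically right is not judged here. Traumatic onset is absent from the variable list and the questionnaire. Unless criterion iv is meant to require a listed finding in every patient, normal morphology and traumatic onset coincide by design.

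The resulting bias in a morphology comparison is (1 − t) times the effect of onset, anywhere from none to all of it. The share of patients without a listed abnormality is unknown. The 0 to 30% range rests wholly on carrying over a rate from coccygodynia patients in general and should not be read as a forecast. Nor can a distortion in a pooled success rate be calculated, because the plan defines no success endpoint and gives no outcome by film status. The pooled before/after comparison for Purpose 1 and its sample size are not invalidated by this; the damage is to Purpose 2.

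**What to change.** 1. The investigators reconcile the background indication, the inclusion criteria (pain severity, and whether the second option of criterion iv also needs a film finding) and the Coccygectomy section.
2. Record traumatic onset (yes/no) at screening for every patient, including those who qualify on film. List it in Definition of Variables as a separate independent variable. It should not be a level of morphology, since a patient can have both an abnormality and a traumatic onset.
3. Give the morphology variable an explicit no-abnormality level.
4. State the Purpose 2 predictor analysis and enter both variables. Say in advance that their interaction cannot be estimated if the fourth cell is empty.
5. Report VAS change and complication rates by entry route (radiographic only, post-traumatic only, both), with numbers and confidence intervals.

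The cost is protocol wording and one baseline field, since trauma history is not a stated data item for all patients. Subgroup intervals will be wide; at a 10% share, power is about 50% with 88 evaluable patients. The results by route should therefore be presented as estimates and not as tests. This needs to be settled before outcomes are seen.

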## **Feasibility of Project**

- A) Time frame: 3 years
- B) Budget:**
  - a. Patients will be compensated \$50 each for completion of the study- \$5000. Patients will be paid \$20 at the first follow-up appointment and an additional \$30 at the final follow-up if their data set is complete.
  - b. SF-36 licensing fees: \$500 for 2 years.
  - c. Total- \$5,500
- C) **Available population:** Senior author is a major referral physician for coccygodynia. Expect to enroll 50 patients per year for 2 years. Previous treatments will be recorded to further characterize the study population and to determine its applicability to the general population of patients with this condition.
- D) **Equipment:** none

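### The plan says its sample represents everyone with coccygodynia, but its own criteria limit it to selected, operated adults at one referral clinic, and nothing recorded would show how they were selected

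*Combined protocol and SAP*

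**What the plan says.** Three statements in the Study Population section bear on this point.

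- **Item a and item b (criteria).** Patients need coccygeal pain for more than 2 months, tenderness on palpation, and either a listed radiographic abnormality or post-traumatic disease. They also need "Failure of conservative treatment methods: 4 weeks of NSAIDS, seat cushion, and rest", and a partial coccygectomy. Coexisting low back pain, total previous coccyx surgery, previous lumbar fusion and age under 18 exclude.
- **Item c (method of selection).** "Patients will be deemed study candidates by the senior author".
- **Item d (representation).** "All subjects presenting to our specialty clinic that meet the selection criteria will be offered enrollment". The next sentence draws the conclusion: "This should represent the total population of patients with this disease".

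The Summary of Study Design adds the source of patients: "All patients will be seen and enrolled through an outpatient spine specialty clinic of the senior author". It also says that a research assistant, as a third party, makes the offer of enrollment. Under Feasibility of Project, item C, the plan says "Senior author is a major referral physician for coccygodynia". It adds there that previous treatments will be recorded, partly to judge how far the cohort speaks for patients with the condition in general.

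**The concern.** Item d gives the sample a property that the design does not provide. The criteria describe a surgical subgroup of one specialist's referred patients, not everyone with the disease. The first stated purpose is to report outcomes and complication rates. With no control group, those rates depend directly on who is in the cohort. A reader who takes item d at face value would apply them too widely.

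Items c and d also describe entry in two ways. If the listed criteria settle who enters, it is not clear what the senior author's judgement adds. If that judgement settles it, the promise to offer enrollment to everyone who qualifies is not assured. The plan describes no count of clinic patients who are not deemed candidates, who decline, or who are operated on outside the study. If patients with a poorer outlook were left out, the reported rates would look better than they should, and nothing recorded would show it.

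**Working it through.** The plan attaches no figure to representativeness, so there is none to reproduce. The check is mainly a comparison of text.

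**1. The claim against the criteria.** The population named in item d is all patients with the disease. The population that can enter is narrowed at each of these steps:

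- attendance at one specialty clinic, that of a referral physician (Summary of Study Design; Feasibility, item C);
- age 18 or over (exclusion iii);
- radiographic abnormality or post-traumatic disease (inclusion iv);
- failed conservative treatment (inclusion v);
- partial coccygectomy (inclusion vi);
- no coexisting low back pain, no total previous coccyx surgery and no previous lumbar fusion (exclusions i and ii).

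Inclusion vi is enough to defeat the claim: patients who never have surgery belong to the disease population but cannot be in the sample.

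**2. One step that the documents let us size.** The Imaging part of the Background cites a series of 582 patients with coccygodynia, 70% of whom had abnormalities on standing and sitting views.

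- Share without abnormality: 1 - 0.70 = 0.30.
- Number: 0.30 × 582 = 174.6, about 175 patients.

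Under inclusion iv, such patients could enter only if post-traumatic. The documents do not say how many were. The share shut out by this criterion in that series is therefore at most about 30%, taking that series' abnormalities to be those listed in inclusion iv.

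**3. Item c against item d.** One item makes candidacy something the senior author deems; the other makes it follow from the criteria. No sentence says which governs when they differ. The research assistant makes the offer, but nothing says that this person screens patients independently.

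**4. What is recorded.** Previous treatments are recorded to characterise the study population. The plan describes no screening log, no reasons for non-entry, and no count of clinic patients operated on but not enrolled. Feasibility, item C, treats wider applicability as something still to be determined, whereas item d asserts it.

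**5. How large a selection effect could be (assumption only).** Let f be the share of eligible operated patients not enrolled, and let s₁ and s₂ be the success rates in those enrolled and not enrolled.

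- Rate in all eligible operated patients = (1 - f)s₁ + f·s₂.
- Excess in the reported rate = f(s₁ - s₂).

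Assume s₁ = 0.90 and s₂ = 0.60:

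- f = 0.10: 0.9 × 0.90 + 0.1 × 0.60 = 0.87; excess 0.03.
- f = 0.20: 0.8 × 0.90 + 0.2 × 0.60 = 0.84; excess 0.06.

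For scale, two surgical series in the Background report good to excellent results in 34/37 = 91.9% and 53/61 = 86.9%, a difference of 5.0 points. The plan defines no success endpoint and gives none of f, s₁ or s₂, so this shows sensitivity and does not estimate bias. The same formula applies to complication rates, which the plan does say it will calculate.

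**The case against.** The case for the plan is substantial. It lists explicit criteria, commits to offering enrollment to every clinic patient who meets them, and has a third party make the offer. Item c can be read as the clinician applying those criteria, in which case it does not conflict with item d. The first purpose concerns patients treated with coccygectomy, so the narrow sample is close to the intended target. No test or sample-size calculation uses the disputed sentence, and recording previous treatments shows that applicability is treated as open.

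Much of this stands, and it rules out several stronger readings that a reader might infer:

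- **That one surgeon alone decides who enters.** The criteria and the third-party offer count against this, and the documents do not say that the senior author performs the operations.
- **That the study repeats a bias it condemns.** The Background faults a cited study because the "decision to treat operatively was made by the senior author leading to significant selection bias". That study compared surgery with injection, and the decision to operate determined the group. This study has no control group, so that bias in a contrast cannot arise. The parallel extends only to the senior author's role in selection.
- **That over-generalisation is certain, or that the rates are biased.** The documents support only that this may happen and could not be checked.
- **That the cited injection results show how few patients remain candidates for surgery.** Failed injection is not an entry criterion, and the non-surgical success figures cited in the Background run from 20% to 85%.

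The objection does not rescue the sentence in item d, which is untrue on the plan's own criteria. Recording the previous treatments of enrolled patients also says nothing about those not enrolled.

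**Conclusion.** The concern holds in a limited form. Item d states a property that the design lacks. Items c and d leave unclear whether criteria or judgement decides entry, and the absence of any count of patients not enrolled means that selection into the cohort could not be assessed. The harm is to the generalisability of the outcome and complication rates, not to a between-group comparison.

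The only size resting on the documents is that about 30% of one cited series lacked radiographic abnormality and could enter only if post-traumatic. The 3 to 6 point excess rests wholly on the assumed 10-20% not enrolled and 60% against 90% success. The documents do not show that any eligible patient will be left out. The point should be fixed before enrollment, because the counts cannot be reliably rebuilt later. It does not invalidate the study.

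**What to change.** 1. **Item d.** Replace the last sentence with: 'Results apply to adults referred to this specialty clinic who meet these criteria and undergo partial coccygectomy.'
2. **Item c.** State that, for study entry, the senior author's clinical findings are used only to apply the listed criteria to consecutive patients. Palpation and reading radiographs need clinical judgement, so this step should not pass to the research assistant.
3. **Log.** Have the existing research assistant list consecutive clinic patients with coccygodynia: met criteria (yes/no), had coccygectomy (yes/no), enrolled (yes/no), and reason if not. A log of operations alone would miss patients never deemed candidates. Report these counts alongside the results.

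The cost is a narrower stated conclusion and a small amount of logging on patients outside the study. Treatment, sample size and analysis do not change.
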